5.6 Study Discontinuation

The NIH, RDCRN DSMB and local IRBs (at their local site) have the authority to stop or suspend this trial at any time. This study may be suspended or closed if:

- Early stopping rules have been met (see section 5.3)
- The study objectives have been met
- The Study Chair / Study Investigators believe it is not safe for the study to continue
- The RDCRN DSMB suspends or closes the trial
- The NIH suspends or closes the trial
- The FDA suspends or closes the trial

5.7 Subject Discontinuation

An intent to treat approach will be used. If participants are unable to tolerate the study drug, the study drug will be stopped, but they will be followed at regular visits until the end of the trial unless they withdraw consent. All data acquired prior to termination for the reasons outlined below will be included in the primary analysis. If participants withdraw from the trial, every effort will be made to conduct a final study visit with the participant and participants will be followed clinically until, if applicable, all adverse events resolve. Reasons for withdrawal from the trial may include:

- Withdrawal of consent by the participant
- Withdrawal by the investigator
- Intercurrent illness or event that precludes further visits to the study site or ability to evaluate disease (e.g. mental status change, large pleural effusion).
-

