4.5 Data Elements

The following laboratory tests and procedures will be used as the primary data elements:

- Erythrocyte protoporphyrin
- Plasma total porphyrins
- A complete blood count with differential
- Iron studies (serum iron, TIBC, Transferrin saturation)

- Serum ferritin
- Hepatic function panel (serum ALT, AST, alkaline phosphatase, total and direct bilirubin, albumin, total protein)
- EPP-specific Quality of Life Questionnaire

These will be completed at each study visit, and an adverse event review will be completed bi-weekly.

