 - Transferrin saturation
 - Hepatic function panel
 - Erythrocyte protoporphyrin levels with metal-free and zinc ratio
 - Plasma total porphyrins
- Two yellow top 10mL ACD tubes will be collected and banked for future RNA and protein studies in this patient population (at 6 month visit only)
- Pill counts will be performed and recorded to monitor compliance
- Old medication bottles will be collected
- Subjects will be discharged with a 3 month supply of medication with some surplus to account for dropped pills.

12 Month Study Visit (Or Early Termination Visit) (+/- 7 days):

- Patients will be admitted to the Clinical Research Unit or a comparable facility for ~2 hours
- A review of systems and physical exam will be performed
- Adverse events will be reviewed
- All concomitant medication changes will be recorded
- Patients will be asked to complete an EPP-specific quality of life questionnaire
- Laboratory studies will include:
 - A complete blood count
 - Serum iron
 - TIBC
 - Serum ferritin
 - Transferrin saturation
 - Hepatic function panel
 - Erythrocyte protoporphyrin levels with metal-free and zinc ratio
 - Plasma total porphyrins
- Two yellow top 10mL ACD tubes will be collected and banked for future RNA and protein studies in this patient population

- A single dose of oral ferrous sulfate (two 325 mg tablets) will be administered with water
- Old medication bottles will be collected and pills will be counted for compliance

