Safety Endpoints: The primary safety endpoints will be an increase in reported clinical symptoms or a 35% increase in erythrocyte protoporphyrin levels. If an increase of 35% over baseline erythrocyte protoporphyrin levels is observed this test will be repeated after 2-4 weeks without discontinuing iron. If the level remains elevated $\geq 35\%$ on repeat testing then the study drug will be discontinued. If clinical symptoms increase to the point where the patient or treating physician is not comfortable continuing then the study drug should be discontinued. The secondary safety endpoints will be any increase in plasma porphyrins and side effects of oral iron therapy such as GI irritation, constipation, diarrhea, nausea, vomiting, and dark stools. If these secondary safety endpoints occur then discontinuing the oral iron will be at the discretion of the treating physician.

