5.9 Quality Control: Study Related Procedures

The standard laboratory measures (CBC, CMP, Iron panel, etc) will be performed at each sites' central laboratory. Erythrocyte protoporphyrin measurements will be performed in the CLIA certified laboratory of [name], University of Texas Medical Branch, Galveston, TX.

The investigational pharmacy at each site will be responsible for drug accountability while the investigators/coordinators will be responsible for compliance of the subjects. The Investigational Drug Service at the Icahn School of Medicine at Mount Sinai will serve as the coordinating pharmacy for this study.

6. Statistical Considerations

The primary outcome is the relative difference in erythrocyte protoporphyrin levels between baseline and 12 months after treatment. A Bayesian approach based on the posterior distribution that the mean relative difference between baseline and 12-month erythrocyte protoporphyrin levels is greater than 0 will be used to assess the strength of potential efficacy of oral iron therapy.

The procedure will be carried out as follows. Let X_0 and X_{12} be the observed mean erythrocyte protoporphyrin level at baseline and 12 months. Let X_0 and X_{12} be correlated with a Pearson correlation coefficient of r and let $d = \frac{X_0 - X_{12}}{X_0}$ and $\Theta = \frac{\mu_0 - \mu_{12}}{\mu_0}$.

Based on data observed in previous studies, we assume that the distribution of

erythrocyte protoporphyrin follows a gamma distribution (see background data section below). For an individual i , $X_{0i} \sim \text{gamma}(\alpha_0, \beta_0)$ and $X_{12i} \sim \text{gamma}(\alpha_{12}, \beta_{12})$.

$X_0 = \frac{\sum_{i=1}^n (X_{0i})}{n}$, therefore $\frac{1}{n} X_0 \sim n * \text{gamma}(\alpha_0, \beta_0) = \text{gamma}(n\alpha_0, \beta_0)$ and likewise $\frac{1}{n} X_{12} \sim \text{gamma}(n\alpha_{12}, \beta_{12})$.

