Two correlated gamma distributions can be generated using a single parameter α , the means of each distribution and the standard deviation as detailed in Ronning et al (23). We specify a non-informative normal($n^*0, 0.01$) prior for α . After data collection the posterior distribution of $\alpha|d \sim \text{normal}(n^* \frac{X_0}{\sigma_0^2/X_0}, 0.01)$. The posterior distribution for $\Theta|d$ can be generated by simulating baseline and 12 month mean values using the posterior distribution of $\alpha|d$, the observed correlation between 12 month and baseline values and the observed standard deviations. After generating the posterior distribution for $\Theta|d$ we will be able to compute the probability that $\Theta|d > 0$.

Prior to any data collection, equipoise implies that the probability that iron therapy will improve erythrocyte protoporphyrin levels (i.e. the relative difference between baseline and 12 months will be greater than 0) is 50%. An increase in this probability to a level providing reasonable assurance of an efficacy signal (e.g. 80%) would warrant additional study of iron. A probability of 80% corresponds to an approximate quadrupling of the odds that iron is effective in lowering erythrocyte protoporphyrin (i.e., from 50% probability of iron's efficacy, or 1:1 odds, to 80% or 4:1 odds).

Sample size justification:

Assuming the distribution of baseline erythrocyte protoporphyrin is gamma (2.3, 861) and that baseline and 12 month values are correlated with $r = 0.7$, simulations indicate that a total sample size of 20 patients will allow us to detect an approximate quadrupling of the odds that iron is effective in lowering erythrocyte protoporphyrin if the true effect size is 10%. Table 2 lists simulated estimates (100,000 runs for each) of the probability that $\Theta|d > 0$ across several sample size and effect size scenarios.

Table 2: Simulation results

r	Sample Size	Effect Size				
		0%	5%	10%	15%	20%
.7	10	0.50	0.63	0.74	0.83	0.90
	15	0.50	0.65	0.78	0.88	0.94
	20	0.50	0.67	0.81	0.91	0.96
	25	0.50	0.69	0.84	0.93	0.97
	30	0.50	0.71	0.86	0.95	0.98
	35	0.50	0.72	0.88	0.96	0.99
	40	0.50	0.74	0.89	0.97	0.99

Background Data

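### Does the plan need a new primary analysis because section 5.7 brings in all pre-termination data while the section 6 statistic uses only baseline and month 12?

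*Combined protocol and SAP*

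**What the plan says.** Section 5.7 (Subject Discontinuation) states an intent-to-treat approach and then: "All data acquired prior to termination for the reasons outlined below will be included in the primary analysis". On follow-up it says: "If participants are unable to tolerate the study drug, the study drug will be stopped, but they will be followed at regular visits", to the end of the trial unless consent is withdrawn. For those who leave the trial, "every effort will be made to conduct a final study visit with the participant".

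Section 6 (Statistical Considerations) defines X0 and X12 to "be the observed mean erythrocyte protoporphyrin level at baseline and 12 months", with d = (X0 − X12)/X0. The gamma sums for the two time points carry the same n. The posterior also needs "the observed correlation between 12 month and baseline values and the observed standard deviations".

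Section 4.6 lists the last visit under one heading, "12 Month Study Visit (Or Early Termination Visit) (+/- 7 days", and erythrocyte protoporphyrin is among its laboratory tests. Of the laboratory tests, which include this one, section 4.5 says: "These will be completed at each study visit". The safety endpoints in section 5.3 say that if a rise of 35% or more persists "on repeat testing then the study drug will be discontinued". The secondary random-effects model in section 6 covers protoporphyrin over time.

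**The concern.** Read literally, the two sections do not meet. Section 5.7 brings every pre-termination value into the primary analysis, but a two-time-point statistic cannot take a month 3, 6 or 9 value from a patient who has no month 12. Three readings seem possible:

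- complete pairs only;
- all baselines against whatever month-12 values exist;
- the early-termination value taken as X12.

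The study is open label with a single arm, so a rule chosen late could be chosen with the result in view. If patients whose protoporphyrin rises, or who do not respond, are the ones lost, complete pairs lean toward iron. The drug-stopping rule in section 5.3 acts on the primary outcome variable, and the follow-up sentence in section 5.7 names only patients who cannot tolerate the drug. At stake is the 80% posterior probability that would justify further study. The planning figure of 0.81 sits only one point above it.

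**Working it through.** **Inputs (section 6).** Baseline gamma(2.3, 861): mean 2.3 × 861 = 1980.3 and SD √2.3 × 861 = 1305.8. Correlation r = 0.7, n = 20, effect 10%, threshold 0.80. No withdrawal rate is given.

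**Plan's own figure.** Normal approximation with equal SDs: P = Φ(1980.3·e / [1305.8·√(2(1 − r))/√n]). The SD of a paired difference is 1305.8 × √0.6 = 1011.5. At n = 20 the standard error is 226.2, so P = Φ(198.0/226.2) = 0.809 against the stated 0.81. Over all 35 cells of Table 2 the largest difference is 0.008.

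**Random loss.** With a 10% fall, 18 pairs give 0.797, 16 give 0.783 and 14 give 0.768. This is lost precision without bias. Table 2 itself moves only from 0.81 (n = 20) to 0.78 (n = 15).

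**A simple informative case.** Take equal baselines, with 17 patients falling 10% and 3 unchanged patients leaving. Pairs give d = 10.0%. All 20 give 17 × 10%/20 = 8.5%.

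- 17 pairs: Φ(198.0/245.3) = 0.790.
- 20 patients at 8.5%: Φ(168.3/226.2) = 0.772.

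Both fall below 0.80. The two readings disagree only in a band. Since Φ(0.8416) = 0.80, pairs reach the mark at 0.8416 × 245.3/1980.3 = 10.4%. All 20 reach it at 0.8416 × 226.2/1980.3 = 9.6%, which is a fall of 9.6 × 20/17 = 11.3% in those who stay. The band is 0.9 points wide, against a standard error for d of 226.2/1980.3 = 11.4 points.

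**A harsher assumed case.** Completers fall 10% and leavers end 35% above baseline.

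| Missing month 12 | Complete pairs | Leavers set to no change | Leavers at +35% used as X12 |
|---|---|---|---|
| 2 of 20 | 0.797 | 0.785 (d = 9%) | 0.685 (d = 5.5%) |
| 4 of 20 | 0.783 | 0.758 (d = 8%) | 0.535 (d = 1%) |

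The rule can matter here, and using the final visit moves the result against iron.

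**Simulation with no effect.** Gamma and lognormal baselines above 400, n = 20, r = 0.7. A confirmed rise of 35% or more occurs in 4.6–5.6 of 20 patients, and an assumed 25% or 50% of these patients have no later visit. Share of trials meeting the 80% criterion:

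| Handling | Equally correlated visits: 25% / 50% lost | Serial correlation: 25% / 50% lost |
|---|---|---|
| Full data | 21–23% | 22–23% |
| Complete pairs | 28–30% / 33–37% | 31–33% / 42–45% |
| Final-visit value as X12 | 22–23% / 21–22% | 22–23% / 21–22% |
| All baselines against observed month 12 | 22–23% / 22% | 27% / 30–33% |

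At an assumed r = 0.85, complete pairs give 25–28% and 30–38%. At an assumed r = 0.95, about one patient per trial triggers, and complete pairs give 23–25% against 21% on full data. With random loss of 10–20%, complete pairs and full data both give 21–24%.

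**The alternative primary.** A repeated-measures model with categorical visit and unstructured covariance over five visits has 5 × 6/2 = 15 covariance parameters for 20 patients. Under the informative loss above it holds the no-effect rate at 19–23%. At a true 10% effect it meets the criterion in 52–55% of trials against 57–58% for pairs with no loss, and in 48–50% against 53–54% with 20% random loss.

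**The case for a change.** The strongest case for a change is textual. The month-12/early-termination heading in section 4.6 is a list of procedures and not an analysis rule, and it carries a 7-day window. It does not say that a value taken at month 4 is X12. A patient who leaves with no final visit is not covered at all. Follow-up after a protoporphyrin-triggered drug stop is unstated, and loss there would depend on the outcome. The planning correlation of 0.7 is close to the 0.74 observed in the longitudinal study, so the simulated trigger rate follows from the plan's own inputs. Settling the rule would need no new data.

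Most of the textual point stands: the rule is not written in the text available, from which a part just before section 4.1 is missing. Less stands on consequence. The all-baselines reading does not fit a statistic with a single n and a paired correlation. Complete pairs is the reading least consistent with section 5.7, yet it supplies most of the large figures. Section 5.3 stops the drug and not the visits, and a protoporphyrin rise is not among the withdrawal reasons that section 5.7 lists, although that list is open. Section 3 also reports little within-patient variation and no documented rise under iron, which sits badly with about 5 of 20 patients showing a confirmed 35% rise under no effect.

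**Conclusion.** This is missing detail that an analyst can fill sensibly from the plan itself. Intent to treat, continued visits after stopping drug for intolerance, the effort to obtain a final visit, and a shared month-12/early-termination visit all point to the last visit's value. In the no-effect model that choice leaves the criterion at 21–23%, the same as full data. Intermediate values still enter the secondary longitudinal model. A patient with no final value can be reported as such, with the result shown under the alternative handling.

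A material bias toward iron needs two things together: dropping incomplete pairs, and an assumed 25–50% loss among patients who rose. The documents give no withdrawal rate and support neither. The true size is therefore unknown; under random loss there is no bias. Sections 5.3 and 5.7 do not contradict each other on follow-up after a protoporphyrin-triggered stop; section 5.7 does not mention that case.

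Replacing the primary method would be a debatable trade. It protects against a loss that may not occur, costs sensitivity when nothing is missing, and still needs a rule for off-schedule early-termination values, which have no cell in a categorical-visit model. For a 20-patient pilot whose criterion only supports further study, no change follows.

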5.8 Data Quality and Monitoring Measures

As much as possible data quality is assessed at the data entry point using intelligent on-line data entry via visual basic designed screen forms. Data element constraints, whether independent range and/or format limitations or 'relative' referential integrity limitations, can be enforced by all methods employed for data input. QA reports assess data quality post-data entry. As we note, data quality begins with the design of the data collection forms and procedures and incorporates reasonable checks to minimize transcription and omission errors. Of the more important quality assurance measures are the internal validity checks for reasonableness and consistency.

- Data Monitoring: The RDCRN DMCC identifies missing or unclear data and generates a data query to the consortium administrator contact.
- Data Delinquency Tracking: The Data Management and Coordinating Center will monitor data delinquency on an ongoing basis.

5.9 Quality Control: Study Related Procedures

The standard laboratory measures (CBC, CMP, Iron panel, etc) will be performed at each sites' central laboratory. Erythrocyte protoporphyrin measurements will be performed in the CLIA certified laboratory of [name], University of Texas Medical Branch, Galveston, TX.

The investigational pharmacy at each site will be responsible for drug accountability while the investigators/coordinators will be responsible for compliance of the subjects. The Investigational Drug Service at the Icahn School of Medicine at Mount Sinai will serve as the coordinating pharmacy for this study.

6. Statistical Considerations

The primary outcome is the relative difference in erythrocyte protoporphyrin levels between baseline and 12 months after treatment. A Bayesian approach based on the posterior distribution that the mean relative difference between baseline and 12-month erythrocyte protoporphyrin levels is greater than 0 will be used to assess the strength of potential efficacy of oral iron therapy.

The procedure will be carried out as follows. Let X_0 and X_{12} be the observed mean erythrocyte protoporphyrin level at baseline and 12 months. Let X_0 and X_{12} be correlated with a Pearson correlation coefficient of r and let $d = \frac{X_0 - X_{12}}{X_0}$ and $\Theta = \frac{\mu_0 - \mu_{12}}{\mu_0}$.

Based on data observed in previous studies, we assume that the distribution of

erythrocyte protoporphyrin follows a gamma distribution (see background data section below). For an individual i , $X_{0i} \sim \text{gamma}(\alpha_0, \beta_0)$ and $X_{12i} \sim \text{gamma}(\alpha_{12}, \beta_{12})$.

$X_0 = \frac{\sum_{i=1}^n (X_{0i})}{n}$, therefore $\frac{1}{n} X_0 \sim n * \text{gamma}(\alpha_0, \beta_0) = \text{gamma}(n\alpha_0, \beta_0)$ and likewise $\frac{1}{n} X_{12} \sim \text{gamma}(n\alpha_{12}, \beta_{12})$.

Two correlated gamma distributions can be generated using a single parameter α , the means of each distribution and the standard deviation as detailed in Ronning et al (23). We specify a non-informative normal($n^*0, 0.01$) prior for α . After data collection the posterior distribution of $\alpha|d \sim \text{normal}(n^* \frac{X_0}{\sigma_0^2/X_0}, 0.01)$. The posterior distribution for $\Theta|d$ can be generated by simulating baseline and 12 month mean values using the posterior distribution of $\alpha|d$, the observed correlation between 12 month and baseline values and the observed standard deviations. After generating the posterior distribution for $\Theta|d$ we will be able to compute the probability that $\Theta|d > 0$.

Prior to any data collection, equipoise implies that the probability that iron therapy will improve erythrocyte protoporphyrin levels (i.e. the relative difference between baseline and 12 months will be greater than 0) is 50%. An increase in this probability to a level providing reasonable assurance of an efficacy signal (e.g. 80%) would warrant additional study of iron. A probability of 80% corresponds to an approximate quadrupling of the odds that iron is effective in lowering erythrocyte protoporphyrin (i.e., from 50% probability of iron's efficacy, or 1:1 odds, to 80% or 4:1 odds).

Sample size justification:

Assuming the distribution of baseline erythrocyte protoporphyrin is gamma (2.3, 861) and that baseline and 12 month values are correlated with $r = 0.7$, simulations indicate that a total sample size of 20 patients will allow us to detect an approximate quadrupling of the odds that iron is effective in lowering erythrocyte protoporphyrin if the true effect size is 10%. Table 2 lists simulated estimates (100,000 runs for each) of the probability that $\Theta|d > 0$ across several sample size and effect size scenarios.

Table 2: Simulation results

r	Sample Size	Effect Size				
		0%	5%	10%	15%	20%
.7	10	0.50	0.63	0.74	0.83	0.90
	15	0.50	0.65	0.78	0.88	0.94
	20	0.50	0.67	0.81	0.91	0.96
	25	0.50	0.69	0.84	0.93	0.97
	30	0.50	0.71	0.86	0.95	0.98
	35	0.50	0.72	0.88	0.96	0.99
	40	0.50	0.74	0.89	0.97	0.99

Background Data

As of March 17, 2015 there were 152 EPP and XLP patients in The Longitudinal Study of the Porphyrias who had an erythrocyte protoporphyrin level >400 , were not on Iron therapy and had no reported liver disease (fibrosis, cirrhosis, steatosis) or liver transplant history. The distribution of these patients' baseline erythrocyte protoporphyrin is pictured in figure 2.

[figure not shown]

Figure 2: Distribution of 152

Data from The Longitudinal Study of the Porphyrias demonstrated that the correlation between erythrocyte protoporphyrin levels taken approximately 1 year apart was 0.74.

Secondary Analyses:

In addition to the primary outcome, the following secondary endpoints will be analyzed:

- 1) Erythrocyte protoporphyrin over time: Mean values and standard deviations will be computed at each time point and values will be compared descriptively. Additionally, a random effects longitudinal model of erythrocyte protoporphyrin with time as the predictor variable will be fit. Time will be treated as a continuous measure unless diagnostic plots suggest that a linear mean function for time is not the correct specification. If this is the case, time (ie visit timepoint) will be treated as a categorical variable. Using the fitted model, we will test the null hypothesis that the beta coefficient(s) for time = 0. There have been no previous studies on the effect of iron therapy on erythrocyte protoporphyrin over time. As such, no estimates of between-subject variability or effect size are available to pre-specify the power of this analysis.

- 2) EPP-specific QOL overtime: To assess whether the subjects' EPP-specific QOL changed during the duration of the study, the mean score and standard deviation will be computed at each time point and compared descriptively.
- 3) Safety Endpoints: Rates of Adverse events will be computed. Safety variables such as physical and other laboratory findings will be analyzed descriptively.

7. Data Management

As much as possible, data quality is assessed at the data entry point using intelligent on-line forms via the DMCC. Data element constraints, whether independent range and/or format limitations or 'relative' referential integrity limitations, can be enforced by all methods employed for data input. QA reports assess data quality post-data entry. As we note, data quality begins with the design of the data collection forms and procedures and incorporates reasonable checks to minimize transcription and omission errors. Of the more important quality assurance measures are the internal validity checks for reasonableness and consistency. In addition to those described above, we propose to build these checks into the initial tables and cross tabulations that should reveal any remaining data quality issues.

All study data will be collected via systems created in collaboration with the RDCRN Data Management and Coordinating Center and will comply with all applicable guidelines regarding patient confidentiality and data integrity.

